### 1. Awareness of elder abuse, sense of responsibility for identifying victims:

- Lack of awareness of elder abuse as a barrier towards identifying victims.
- Perceived responsibility of the health care services as well as different health care professions to identify victims of elder abuse
- Case vignette, measuring awareness and propensity for asking patients questions about abuse.

### 2. Perceived ability to ask questions about abuse:

- Self-efficacy for asking questions about elder abuse.
- Cause for concern that asking questions will a) lead to a negative reaction from the patient b) negatively impact the patient-provider relationship

### 3. Preparedness to manage cases of elder abuse

- Self-efficacy for managing the response
- Cause for concern that I will not be able to offer the patient a good follow up
- Collegial support
- Knowledge about proper documentation routines
- Knowledge about judicial concerns

### 4. Preparedness at the clinic to care for older adults subjected to abuse

- Deficient routines
- Preparedness in the clinic and in society

### **Other outcome measures:**

Anonymous data will be drawn from the medical records. It will consist of the number of time elder abuse have been recorded in the designated place in the digital medical record for each participating clinic. The validity of this data has not been established and it will therefore be considered an experimental outcome but could potentially be an objective assessment of whether the intervention leads to increased identification of patients subjected to elder abuse.

Some items in REAGERA-P does not directly measure any of the learning objectives of the education but could potentially be affected by the intervention and will hence also be considered. They are as follows:

- Proportion of respondents reporting that victims of elder abuse were given an adequate follow up.
- Proportion of respondents reporting suspecting elder abuse but refraining from asking questions.
- Proportion of respondents reporting changed working practice at follow up because of the education.

**Covariates** potentially affecting both the intervention effectiveness and the outcome will be considered. These include background characteristics of participants both on an individual and group level.

### **Eligibility**

All health care professionals participating in the education at each clinic are eligible to participate in the study. Hence, for example a respondent belonging to cluster 4, that participate in data collection at step one but do not attend the education at step 3 (when he or she would be expected to attend) will be excluded. On the other side, a respondent from cluster 4 that do not respond to the baseline survey will still be included in the study as long as he or she attend the education at step 2.

Personnel working solely administratively will be excluded.

### **Sample size**

Cluster sample size was calculated using the Shiny CRT Calculator web application (Karla Hemming, Kasza, Hooper, Forbes, & Taljaard, 2020). Significance level was set to 0.05 and power to 0.8. We planned for a three-step intervention and used the discrete time decay. Initially we had planned a complete four period stepped wedge design and hence, that was used in the sample size calculation together with the discrete time decay. Divergent cluster sizes were expected and coefficient of variation for a cluster size was set at 0.5. Results from a pilot study (Johanna Simmons, Motamed, Ludvigsson, & Swahnberg, 2022) was used to estimate cluster auto correlation at 0.6. Proportion

was set as outcome, and we used data from the pilot study to estimate the proportion under control at 0.26 and the proportion under intervention at 0.56. A cluster size of 10 then suffice to reach adequate power. Our smallest expected cluster has 31 participants and hence even with a response rate of less than 40% this is sufficient.

## Statistical analysis

The background characteristics of participants will be explored using descriptive statistics and comparisons will be made between clusters to detect significant differences. Missing data will be analysed and, if appropriate, multiple imputations will be considered. Attrition analysis will be conducted using e.g., chi square test and student's t-test to detect differences between those lost to follow up and those retained.

In a stepped wedge trial, results are compared across unexposed and exposed observation periods in the clusters, similar to the control and intervention arm in a parallel cluster trial (K Hemming, Haines, Chilton, Girling, & Lilford, 2015). The primary effect of this study will hence be calculated by comparing the main outcome (propensity to ask questions about abuse) in all clusters pre-intervention with all clusters post-intervention. Both mean difference in reported frequency of asking questions and changes in proportion of participants that report ever having asked questions about abuse will be reported. For the continuous outcome a linear mixed effect model will be used and for the binary outcome a generalised linear mixed effect model. The models will consider repeated measures and include cluster as random effect to determine if the anticipated effect of the model is dependent on the cluster, i.e., unit or clinic. During a stepped wedge trial more and more clusters will gradually transition from unexposed to exposed status, meaning that observation in the exposed status will on average be of a later date than the unexposed observation (K Hemming et al., 2015). This may introduce a bias in the study considering that there may be underlying temporal trends affecting the outcome, e.g., an increasing awareness of elder abuse in society over time. Therefore, both intervention status and time will be included as fixed effects in the models. Also, models will be adjusted for covariates, e.g., background characteristics, significantly associated with the outcome.

[figure not shown]
We propose that the education will work by participants overcoming personal and organizational barriers towards asking older patients questions about abuse. The items in REAGERA-P used to evaluate the effect on the different barriers and facilitators are described in figure 1 and they will be included in linear models (for continuous outcome) and generalised linear models (for binary

outcomes) to determine the effect of the intervention on these outcomes. If results support the theoretical model, efforts will be made to test if changes in perceived barriers mediate a potential effect of the intervention on the primary outcome, i.e., asking questions about abuse.

[figure not shown]
Data from the medical records will be retrieved for the following periods a) 6 months pre-intervention, b) 0-6 months post intervention and c) 6-12 months post intervention. A linear mixed effect model will be used to investigate changes concerning how many victims are identified pre- and post-intervention at the participating clinics.

In all models, we will strive for parsimony; analysis will therefore be performed to determine which variables to include in multivariate analysis and only covariates that significantly affect the model will be included. Assumptions for models will be assessed graphically and, if needed, bootstrapping will be used to ensure model robustness. Significance level will be set at  $p=0.05$  and results will be reported with 95% confidence intervals.

**Figure 1.** Theoretical model. An illustration of the alignment between learning activities (yellow), learning objective, that is, barriers and facilitators on a personal (green) and organisational (blue) level as well as evaluation (red). EA, elder abuse; REAGERA-P, Responding to Elder Abuse in GERiatric care—Provider questionnaire.

**Figure 2** Design of the study and data collection points. An incomplete stepped wedge trial is planned. All clusters are measured pre-intervention (yellow squares=baseline and in conjunction with the educational day) and post-intervention (blue squares=at 6–8 months and 12–14 months of follow-up). Time of intervention is denoted by the red contour.

*Note: All health care providers participating in the education are eligible to participate in the study, e.g., a person belonging to cluster 4 that do not respond to the baseline (period 1) survey but later partake in the education (period 3) will be asked for inclusion. Meanwhile, a respondent belonging to the same cluster, that participate in the data collection at baseline, but do not attend the education will be excluded. The total anticipated number of participants is around 700. \* Originally planned number of participants in cluster 8 was n=60. However, the primary care center decided against scheduling all employees, instead those wanting to participate had to register for it and only seven professionals did so*

*\*\* Originally cluster 6 was planned to be a geriatric clinic and cluster 9 was planned to be a large primary care center. The clinics however decided to not participate and were therefore replaced by a smaller primary care center (new cluster 6) and a cluster open to staff from various primary care centers (cluster 9).*

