## Study design:

The design is a non-randomised stepped wedge trial, a type of controlled cluster cohort study in which the participants gradually move from control group to intervention group (Brown & Lilford, 2006; Copas et al., 2015). In this study, a cluster entail a whole clinic or a unit at a clinic and at the end of the study all clusters will have completed the intervention, i.e., participated in the education. Data will be collected for all participants both pre- and post-intervention. Figure 2 illustrates the study design, including time plan. The intervention was originally planned to be rolled out during four periods between September 2021 and June 2023 (figure 2) and an incomplete design was chosen, i.e., six periods are used, but every cluster is only included at four measurement points: at baseline, in conjunction with the education, at six months follow up and at twelve months follow up. Similar incomplete designs have been described previously (Copas et al., 2015; Karla Hemming, Lilford, & Girling, 2015). For practical reasons the primary care centres included in the first study period had to be included later than the hospital clinics, i.e., in December 2021. To avoid a data collection period during the summer vacation, their first follow up was conducted nine months post intervention. Thereafter they will fall into the same pattern of data collection at six months interval as the other clinics. The six months interval was chosen because it provides an intermediate (six months) and long-term (twelve months) follow up that allows for a reasonable evaluation of the effect of the education. The times of data collection is illustrated in figure 2.

One geriatric clinic (cluster 8) and one primary health care centres (cluster 9) who were included at baseline decided in 2023 not to participate in the study for logistic reasons, e.g., having to prioritize other training for the staff. Therefor another primary health care centre was included (new cluster 8) and one training day was also open to participants from various primary health care centres (new cluster 9). For these clusters there is therefore no baseline data available, only pre-intervention data. In addition, the data collection phase had to be prolonged until September 2023.

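### With apparently nine clusters, the plan names no small-sample inference method and no cluster-by-period effect, so its tests may reject too often, most clearly for the binary main outcome

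*Combined protocol and SAP*

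**What the plan says.** The Statistical analysis section assigns a linear mixed model to the number of times a professional has asked about abuse, and a generalised linear mixed model to ever having asked. On the random part it says: "The models will consider repeated measures and include cluster as random effect". Intervention status and time are fixed effects. The last paragraph of the section sets the significance level at 0.05 and says that "results will be reported with 95% confidence intervals". After graphical checks of model assumptions it adds that "if needed, bootstrapping will be used to ensure model robustness". The type of bootstrap, the resampling unit and the trigger are not given.

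The text states no total number of clusters. The highest number in Study design and in the note to Figure 2 is nine. The note puts one cluster at seven participants and the total at around 700. Study design says that "six periods are used, but every cluster is only included at four measurement points", and that the two replacement clusters have no baseline.

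The Sample size section says "Significance level was set to 0.05 and power to 0.8" and "We planned for a three-step intervention and used the discrete time decay". It uses pilot data to "estimate cluster auto correlation at 0.6". It gives no intracluster correlation.

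**The concern.** The effect of the education is judged against variation between clusters and, if clusters drift, against variation between periods within a cluster. Both variances would be estimated from about nine clusters. Limits of estimate plus or minus 1.96 standard errors treat them as known, and maximum likelihood also tends to underestimate them. The resulting intervals are too narrow and the p-values too small.

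The sizing assumption makes drift relevant. A cluster autocorrelation of 0.6 means that a cluster's level in one period is only partly shared with its level in another. A model with a single constant cluster effect cannot represent this. At stake are the p-value and interval that decide aim 1, in particular for the binary form, on which the trial was sized.

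**Working it through.** **1. The plan's own figure.** The stated result is that 10 per cluster gives power 0.8 at 0.05. It cannot be reproduced uniquely, because neither the ICC nor the number of clusters is given. Using generalised least squares for a complete three-step, four-period design (proportions 0.26 and 0.56, autocorrelation 0.6 with discrete time decay, size coefficient of variation 0.5, two-sided test) and an assumed nine clusters of 10:

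| ICC (assumed) | Power, normal limits | Power, t on 7 df |
|---|---|---|
| 0.01 | 0.94 | 0.86 |
| 0.02 | 0.92 | 0.83 |
| 0.05 | 0.87 | 0.76 |
| 0.10 | 0.80 | 0.67 |
| 0.20 | 0.69 | 0.56 |

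The stated figure is consistent with an ICC up to about 0.10 if normal limits are used.

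**2. How much information there is at cluster level.** Nine clusters at four points give at most 9 × 4 = 36 cluster-periods. Two lack a baseline, which leaves 34. If the two or three first-step clusters have baseline and education in the same period, 32 or 31 remain. Subtracting 9 clusters, 5 period contrasts and 1 intervention contrast gives 36 − 15 = 21 down to 31 − 15 = 16 degrees of freedom. The cautious convention is clusters minus 2 = 7. The chance that a t variable exceeds 1.96 in absolute value is 6.3% at 21 df, 6.8% at 16 df and 9.1% at 7 df.

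**3. Simulated rejection rates with no true effect.** Set-up: nine clusters, six periods, and four measurements per cluster. Sizes were either 78 each, or uneven from 7 to 120 totalling 700 with two clusters lacking a baseline. Assumed: ICC 0.02-0.10, exchangeable cluster-by-period effects, and within-person correlation 0.5 in the linear model. The binary model was a logit fit with base rate 0.26 and no participant effect. There were 800 runs (linear) or 600 (binary) per main setting. The Monte Carlo standard error is √(0.05 × 0.95/800) = 0.8 points for the linear model and √(0.05 × 0.95/600) = 0.9 points for the binary model near 5%, and up to 1.8 points at the higher rates.

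| Fitted random effects | True autocorrelation | Linear, 1.96 limits | Binary, 1.96 limits |
|---|---|---|---|
| Cluster only | 1 (constant) | 4.9% (ICC 0.05) | 5.7-6.8% (ICC 0.05) |
| Cluster + cluster-by-period | 0.6 | REML 5.5-7.9%, ML 10.6-11.1% (ICC 0.05) | 9.3-12.3% |
| Cluster only | 0.6 | 33-38% (ICC 0.05) | 12-29% |

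Simulations of cluster-period proportions, with a normal approximation, agree on the second row: about 6-9% with REML and about 8-13% with ML. One uneven-size REML setting reached 10.2%. For a true constant cluster effect they give about 5-8%. For the third row they give lower figures, 8-24%, so the excess there depends strongly on the set-up.

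**4. What a correction achieves.**
- With a cluster-by-period term fitted and autocorrelation 0.6, t on 7 df brings the binary model to 4.2-6.3%. It takes the linear REML model to 2.2-2.9% (ICC 0.05), which is conservative.
- A t reference on 16-17 df brings linear REML to 4.8-5.7% (ICC 0.05-0.10, cluster-period simulation).
- With a cluster intercept only and autocorrelation 0.6, t on 7 df still leaves 24-28% (linear, ICC 0.05) and 6-22% (binary). The cluster-period simulation leaves 3-17%.
- With a constant cluster effect, t on 7 df gives 1.2-1.5% (linear) and 2.0-2.7% (binary) at ICC 0.05.

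The Kenward-Roger and Satterthwaite methods were not simulated. The fixed 16-17 df stand in for them.

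**The case against.** The strongest reply is that the plan does not commit to uncorrected inference. It is silent, and the eventual analysis could use REML with a degrees-of-freedom correction. That stands: the finding is that no method is specified, and the documents do not show that none will be applied.

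A reader might infer that this trial's false-positive rate is 6-9% or 8-13%. The documents do not support that. They give no ICC, estimation method, reference distribution or allocation of clusters to steps, and nine clusters is itself inferred from the numbering. The rates also belong to a model with a cluster-by-period term, which the plan does not name. Read literally, with a constant cluster effect that is also true, the plan's linear model is close to nominal and the binary excess is small. The lower end of the linear REML range cannot be told apart from 5% in runs of this length.

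A reader might also infer that a degrees-of-freedom sentence settles the matter whatever random effects are chosen. It does not: with drift present and only a cluster intercept fitted, most of the excess comes from the missing term.

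Finally, the bootstrap should not be written off. A parametric bootstrap that regenerates the cluster-level effects is a legitimate small-sample method. The difficulty is that the plan's wording is conditional, names no type, and is prompted by assumption checks.

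**Conclusion.** The concern holds in conditional form. The plan tests its main outcome with mixed models on apparently nine clusters, one of seven people, and specifies neither a small-sample method nor a cluster-by-period effect, although its own sizing assumes an autocorrelation of 0.6. Under that value, an assumed ICC of 0.02-0.10 and a fitted cluster-by-period effect, normal-limit tests reject about 6-9% of the time (linear, REML) and about 8-13% (binary, ML-type fit).

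The direction is clearest for the binary outcome, which exceeded 5% with normal limits in every binary-model setting simulated at autocorrelation 0.6. The linear REML excess is modest. The choice of random effects and the choice of reference distribution have to be made together. Confidence is medium, because the ICC, the number of clusters and the estimation method are assumptions.

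**What to change.** In Statistical analysis, prespecify:

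- **Random effects:** cluster, cluster-by-period and participant, in line with the autocorrelation in Sample size.
- **Linear model:** REML with Kenward-Roger or Satterthwaite degrees of freedom.
- **Binary model:** one of three, named in advance: interval and p-value from a t reference with clusters minus 2 degrees of freedom; restricted pseudo-likelihood with Kenward-Roger; or a parametric bootstrap that regenerates the cluster and cluster-by-period effects.
- **Number of clusters:** state the total and how the mixed-centre cluster counts. Study design describes the replaced clusters as 8 and 9, while the note to Figure 2 says 6 and 9. The two places need reconciling.

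The cost is a few sentences and standard software options. From the reference distribution alone, intervals widen by 2.120/1.960 = 1.08 (t on 16 df) to 2.365/1.960 = 1.21 (t on 7 df). The cluster-by-period term widens them further where clusters do drift. The t reference on 7 df is somewhat conservative when between-cluster variance is small or constant over time. Naming the method in advance also removes a later choice among ML, REML, normal, t and bootstrap results.

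### The trial is sized for clinic levels that drift between periods, but the primary models commit to no term for that drift; with cluster and participant intercepts alone, the 95% CI would be too narrow

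*Combined protocol and SAP*

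**What the plan says.** The Sample size section takes its correlation structure from a stepped wedge calculator and its inputs from a pilot study. The pilot was "used to estimate cluster auto correlation at 0.6". A complete four-period design had first been planned, and "that was used in the sample size calculation together with the discrete time decay". The section also states that the "coefficient of variation for a cluster size was set at 0.5". No ICC and no number of clusters per step are given.

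The Statistical analysis section specifies a linear mixed model for the number of times asked and a generalised linear mixed model for ever having asked. On random effects it says: "The models will consider repeated measures and include cluster as random effect". The same sentence gives a purpose for the cluster effect: the models are to "include cluster as random effect to determine if the anticipated effect of the model is dependent on the cluster". Time and intervention status are fixed effects. The same section sets a 5% level and 95% intervals, and allows bootstrapping if needed, with no trigger and no resampling unit.

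The design is a cohort. Under Study design: "Data will be collected for all participants both pre- and post-intervention".

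**The concern.** A random intercept for cluster treats a clinic's level as constant over the whole study. The pre/post contrast within a clinic is then assumed free of clinic-level noise. The sizing assumption says otherwise: with autocorrelation 0.6, part of a clinic's level is replaced from one period to the next, and that part does not cancel from the contrast. A participant intercept removes stable differences between people but does nothing about drift shared by everyone in a clinic. If the fitted model has only these two terms, the standard error of the intervention effect omits a source of variation the plan itself expects. The stated 5% level and 95% coverage for the main outcome would then not be met, and the choice of structure would be made after the data are seen.

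**Working it through.** **The plan's own figure.** The Sample size section finds 10 per cluster sufficient. Using the generalised least squares variance of the effect, cluster covariance ICC × σ² × 0.6^|s−t|, σ² = (0.26×0.74 + 0.56×0.44)/2 = 0.2194, and power = Φ(0.30/SE − 1.96) in the complete four-period design with equal sizes, three clusters per step give power 0.97, 0.92, 0.86, 0.80 and 0.76 at ICC 0.01, 0.05, 0.10, 0.15 and 0.20. Two clusters per step reach 0.80 at ICC 0.042. So 10 is attainable but cannot be uniquely reproduced without the ICC and the cluster count.

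**Inputs for the check.**
- From the documents: autocorrelation 0.6; 31 per cluster ("Our smallest expected cluster has 31 participants"); 10 per cluster as the stated sufficient size; proportions 0.26 and 0.56; six periods with four measurements per cluster.
- Assumed: nine equal clusters, three educated in each of periods 2, 3 and 4; 0.6 applied per period; within-person correlation ρ = 0.5; ICC 0.01, 0.05 or 0.10.

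**Hand calculation.** Take the change in a clinic's mean between two adjacent periods, in units of σ², with the same m people answering twice:
- person-level noise: 2(1 − ICC)(1 − ρ)/m = (1 − ICC)/m at ρ = 0.5
- drift: 2 × ICC × (1 − 0.6) = 0.8 × ICC

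If the model counts only the first part, model SE / true SE = √[noise/(noise + drift)], and type I error = 2Φ(−1.96 × ratio).

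| m, ICC | noise | drift | ratio | type I error |
|---|---|---|---|---|
| 10, 0.01 | 0.0990 | 0.008 | 0.96 | 5.9% |
| 31, 0.01 | 0.0319 | 0.008 | 0.89 | 8.0% |
| 31, 0.05 | 0.0306 | 0.040 | 0.66 | 19.7% |
| 31, 0.10 | 0.0290 | 0.080 | 0.52 | 31.2% |

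**Full calculation.** The expected REML criterion was minimised for each working model on the six-period layout, and its model SE compared with the SE under the true covariance (z reference, linear model). With cluster and participant intercepts, type I error is 6.0% at 10 per cluster and ICC 0.01, and 8.5, 21.5 and 33.0% at 31 per cluster and ICC 0.01, 0.05 and 0.10. Adding cluster-by-period gives 4.7, 4.5 and 4.4% at 31 per cluster. With autocorrelation 1, the two-intercept model returns to 5.0%, so the excess comes from the omitted drift.

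**Sensitivity of the two-intercept model** (linear, except the last item):
- Autocorrelation 0.8, 31 per cluster: 7, 15 and 24%.
- Within-person correlation 0.3 or 0.7, 31 per cluster, ICC 0.05: 17 or 29%.
- Unequal assumed sizes (mean 31, one cluster of 7, two without baseline), REML simulation with 2,000 replicates: 8.9, 23.4 and 35.9%; with cluster-by-period, 5.2, 5.9 and 5.9%.
- One or two first-step clusters for which "their first follow up was conducted nine months post intervention": a change of under 1 point.
- Binary model, simulated, 31 per cluster: about 6, 13 and 20%.

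**Interval width.** On the linear approximation to the proportion, with z for both models, 31 per cluster and ICC 0.05, the half-width is 7.7 points with two intercepts and 12.3 with cluster-by-period added (SE 7.7/1.96 = 3.9 against 12.3/1.96 = 6.3; ratio 1.6).

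**The case against.** The strongest reply is that the text is open rather than wrong. Clusters are also measured repeatedly, so a cluster-by-period or autoregressive term would fit the promise to consider repeated measures, and intervals would then be close to nominal. That stands. A reader might infer that no admissible reading matches the sizing assumption, or that the 95% interval is already shown to fail; the documents do not support either. What remains is that the plan does not commit to such a term.

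A reader might also infer that intervals could be too wide, by taking cluster as the only random effect. That model ignores within-person correlation and fits poorly with a cohort and a promise to handle repeated measures, so no weight is put on it. If the purpose clause means an intervention effect that varies by cluster, the linear figures at 31 per cluster fall to about 7, 10 and 12%: smaller, but still above 5%.

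The magnitudes rest on assumed inputs, and this too stands. The 0.6 was set for a complete four-period design whose period length is not stated. Study design mentions roll-out over four periods, while Sample size uses three steps. The note to Figure 2 reports a cluster of seven, below the expected minimum of 31. The error rates are illustrations, not estimates for this trial.

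Finally, switching to t on 7 df widens the 12.3-point half-width to 14.8. That extra 2.5 points comes from the reference distribution, not the missing term, so a danger zone of 8 to 15 points would overstate this concern.

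**Conclusion.** The point holds as a gap between sizing and analysis. Under the plan's own autocorrelation, the natural cohort model gives intervals that are too narrow, and nothing in the text commits the analysts to a model that does not. In the linear illustration at 31 per cluster, the error rate is 8.5 to 33% across ICC 0.01 to 0.10. It is milder for the binary model, about 6% for the linear model at 10 per cluster and ICC 0.01, and absent if autocorrelation is 1.

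In the ICC 0.05 example, observed differences of roughly 8 to 12 points could wrongly appear significant. A reader might infer that the planned 30-point effect is in doubt. It is not: with cluster-by-period and t on 7 df, linear-scale power at 31 per cluster is 100, 99 and 91% at the three ICCs. This should be fixed before analysis. Confidence in the direction is good on the two-intercept reading; confidence in the size is limited by the missing ICC, cluster count and response per wave.

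**What to change.** In the Statistical analysis section, specify random effects for participant, cluster and cluster-by-period (or the discrete-time decay used for sizing) in both primary models. Fix in advance a small-sample method suited to about nine clusters: for example Kenward-Roger or Satterthwaite for the linear model, and a pre-specified t reference for the binary model. The exact degrees of freedom for the binary model are a matter of judgement. Clusters minus two (7) is one option; on the linear scale it is conservative, at about 2 to 3%.

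If bootstrapping is kept, state its trigger and resample whole clusters; resampling participants does not capture drift. If the aim is to learn whether the effect differs between clusters, add a cluster-by-intervention random effect or report cluster-specific effects, because a random intercept cannot show this.

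The cost is wording and one or two variance terms, with no new data. Intervals widen: against the two-intercept model at 31 per cluster, the SE rises by a factor of about 1.15, 1.6 and 2.0 at ICC 0.01, 0.05 and 0.10. Linear-scale power for the planned effect with t on 7 df at 10 per cluster is 96, 89 and 79%, so only the last falls just below the 80% target. Calibration of the binary test with so few clusters remains approximate.
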